5.3.4 Sensitivity Analyses for Primary Endpoint

Following sensitivity analysis to the primary estimand of the primary PFS after randomization will be performed:

- i. **PFS assessed by investigator based on unstratified analysis:** To assess the impact of stratification (as entered in IxRS, see Protocol section 4.2.1) the main analysis described in section 5.3.2 will be repeated without stratification factors.
- ii. **PFS assessed by Independent Review committee (IRC):** To assess the concordance of PFS assessment by investigators PFS analysis, as mentioned in section 5.3.2, will be repeated based on IRC assessment. The IRC cannot evaluate patients if the baseline scans were missing hence in such cases data will be censored at randomization plus 1 day.

- iii. **PFS assessed by investigator based on interval censoring approach:** The impact of missing scheduled tumor assessments on PFS will be assessed by performing sensitivity analysis based on the interval censoring method as described in section [5.3.3](#).

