1.1 OBJECTIVES AND ESTIMANDS

This study will evaluate the efficacy and safety of GDC-9545 30 mg PO QD administered on Days 1-28 of each 28-day cycle, beginning on Day 1 of Cycle 1 compared with physician's choice of endocrine monotherapy in patients with previously treated estrogen receptor (ER)-positive, HER2 negative locally advanced or metastatic breast cancer who have received one or two prior lines of systemic therapy in the locally advanced or metastatic setting. Endocrine monotherapy is defined as either fulvestrant or an aromatase inhibitor.

The primary comparison of interest is the hazard ratio of progression-free survival. The primary trial objective is to demonstrate superiority of the GDC-9545 arm over the physician's choice of endocrine monotherapy treatment arm.

Specific objectives and corresponding endpoints for the study are outlined below.

Table 1: Objectives and Corresponding Endpoints

Primary Efficacy Objective	Corresponding Endpoint

The primary efficacy objective for this study is to evaluate the efficacy of GDC-9545 compared with physician's choice of endocrine monotherapy on the basis of Progression-free survival (PFS).	
Progression-free survival (PFS), defined as the time from randomization to the first occurrence of disease progression or death from any cause (whichever occurs first), as determined by the investigator according to Response Evaluation Criteria in Solid Tumors, Version 1.1 (RECIST v1.1)

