5.3.1 Definition of Primary Estimand

Following the estimand framework introduced in the ICH-E9 addendum ([ICH 2020](#)), the attributes of the estimand built around the primary endpoint are defined as follows:

- **Population:** Patients with previously treated estrogen receptor (ER)-positive, HER2-negative locally advanced or metastatic breast cancer who have received one or two prior lines of systemic therapy in the locally advanced or metastatic setting, as defined by the inclusion / exclusion criteria in study protocol (refer to Protocol section 4.1)
- **Variable:** Progression Free Survival (PFS), defined as time after randomization to the first occurrence of disease progression or death from any cause (whichever occurs first), as determined by the investigator according to RECIST v1.1
- **Treatment:** GDC-9545 or physician's choice of endocrine monotherapy. During the conduct of the study, participants may also receive concomitant medications as detailed in Protocol section 4.4.

- **Intercurrent events and Handling Strategy:**
 - Use of any non-protocol anti-cancer treatment (NPT) prior to disease progression as detailed in Protocol section 4.4.3. → Following treatment policy the ICE will be ignored and tumor assessment data collected after the ICE will be included in the PFS analysis
 - Discontinuation of study treatment prior to disease progression → Following treatment policy the ICE will be ignored and tumor assessment data collected after the ICE will be included in the PFS analysis.
- **Population-level summary:** Hazard ratio

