5.3.2 Main Analytical Approach for Primary Estimand

If participants have any intercurrent event(s), then the strategies defined as defined in section 5.3.1 to handle the intercurrent events will be implemented. Otherwise, data for participants without the occurrence of disease progression or death as of the clinical cutoff date (CCOD) will be censored at the time of the last tumor assessment prior to the CCOD (or at the time of randomization plus 1 day if no tumor assessment was performed after the baseline visit). PFS will be compared between treatment arms using the stratified log-rank test. The hazard ratio will be estimated using a stratified Cox proportional hazards model. The 95% CI for the hazard ratio will be provided. The stratification factors used will be the same as the randomization stratification factors (as entered in IxRS, see Protocol section 4.2.1). Results from an unstratified analysis (see section 5.3.4) will also be provided. For each treatment arm, Kaplan-Meier methodology will be used to estimate the median PFS, and the Brookmeyer-Crowley method will be used to construct the 95% CI for the median PFS. Kaplan-Meier curves will also be produced.

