5.3.3 Handling of Missing Data

The impact of missing scheduled tumor assessments on PFS will be assessed depending on the number of participants who missed assessments scheduled immediately prior to the date of disease progression per RECIST v1.1 or the data cutoff. If > 5% of participants missed two or more assessments scheduled immediately prior to the date of disease progression per RECIST v1.1 or the data cutoff in any treatment arm then the impact of missing scheduled tumor assessments on PFS will be assessed by performing a sensitivity analysis based on the interval censoring method.

For each participant in both treatment arms, the left and the right boundaries of the intervals will be derived based on the following rules:

Situations	Left Boundary	Right Boundary
Participants who had disease progression prior to death	The date of the last assessment that showed a progression-free* ¹ status	The date of the first assessment that showed disease progression
Participants who died without disease progression	The date of the last assessment that showed a progression-free* ¹ status	Death date
Participants who did not die nor had disease progression* ²	The date of the last assessment that showed a progression-free* ¹ status	Not applicable (Missing)

*¹ For participants who did not have any post-baseline assessment with progression-free status, the left boundary is the date of randomization.

*² Including participant withdrawing consent prior to disease progression

The PFS survival curves will be estimated using the nonparametric maximum likelihood estimate (NPMLE, Turnbull 1974) for each treatment arm. The median PFS of each treatment arm will be reported and its 95% confidence interval will be constructed based on the [Brookmeyer-Crowley](#) method ([Brookmeyer and Crowley 1982](#)).

Hypothesis testing will be performed based on the stratified log-rank test proposed by Sun ([Sun 1996](#)) to compare the PFS in the treatment arms. The treatment effect will be estimated using a stratified proportional hazard regression model ([Finkelstein 1986](#)) with a parametric assumption of piecewise exponential distribution for the baseline hazard function ([Friedman 1982](#), [Royston and Parmar 2002](#)). Results from an unstratified analysis will also be provided.

The analyses listed above will be performed using the procedures PROC ICLIEFTTEST and PROC ICPHREG in SAS version 9.4 or a later version.

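### As worded, the IRC sensitivity analysis of PFS censors patients without baseline scans one day after randomization even if they died, which contradicts the SAP's own PFS definition; the effect is small

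*SAP*

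**What the plan says.** The SAP defines PFS in Table 1 (section 1.1) as time to "the first occurrence of disease progression or death from any cause (whichever occurs first"), and section 5.3.1 uses the same event definition for the primary estimand.

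Section 5.3.2 sets the censoring rule: "data for participants without the occurrence of disease progression or death as of the clinical cutoff date (CCOD) will be censored" at the last tumor assessment before the cutoff, "or at the time of randomization plus 1 day if no tumor assessment was performed after the baseline visit". The day-1 date is thus a fallback inside a group that has already been restricted to patients with no event.

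Section 5.3.3 gives interval boundaries for a sensitivity analysis. There is a separate row for "Participants who died without disease progression", with the death date as right boundary. If no post-baseline assessment showed the patient to be progression-free, "the left boundary is the date of randomization".

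Section 5.3.4(ii) states that the 5.3.2 analysis "will be repeated based on IRC assessment", and then adds: "The IRC cannot evaluate patients if the baseline scans were missing hence in such cases data will be censored at randomization plus 1 day".

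**The concern.** The reason given for day-1 censoring is that the IRC has nothing to compare later scans with. That justifies not assigning an IRC progression. It does not justify ignoring a death, which is known from follow-up and needs neither a reader nor a baseline image. The sentence is triggered by missing scans, not by the absence of an event, so a programmer who follows it literally will censor a patient who is known to have died.

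The trial is open-label and the primary endpoint is assessed by the investigator. Of the three sensitivity analyses listed in 5.3.4, the unstratified and interval-censoring analyses both keep the investigator's assessment; only the IRC analysis changes the reader. Its stated purpose is to check concordance with the investigators. If the same death can be an event in the main analysis and a day-1 censoring in the IRC analysis, part of any difference between the two will have nothing to do with how the images were read.

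**Working it through.** **Comparison of the rules.** Take a patient whose baseline scans are missing at the IRC, who has no IRC-assessable disease status, and who dies before the clinical cutoff date (CCOD).

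| SAP section | Treatment of the death |
|---|---|
| 1.1 and 5.3.1, definition | PFS event |
| 5.3.2, main analysis | Event at the date of death, unless investigator-assessed progression came first; the day-1 rule cannot apply because it covers only event-free patients |
| 5.3.3, interval censoring | Event; right boundary is the death date, left boundary is randomization if no progression-free assessment exists |
| 5.3.4(ii), IRC analysis | Censored one day after randomization, as worded |

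The last row is the only one that removes a death, and no other section of the SAP or protocol restores it.

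**Design figure, for scale.** SAP section 3 gives 166 events, 80% power, two-sided 5%, hazard ratio 0.647, 1:1 allocation.

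- Events (Schoenfeld): 4 × (1.960 + 0.842)² / (ln 0.647)² = 166.
- Power at 166 events: Φ(√166/2 × |ln 0.647| − 1.960) = 80.1%.
- Largest significant hazard ratio: exp(−2 × 1.960/√166) = 0.738.

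All three agree with the SAP. The point disputes none of them.

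**Deaths lost.** Deaths lost = 300 × (proportion without a central baseline) × (proportion dead at the cutoff).

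- Proportion without a central baseline: not in the documents. Assumed 3% to 5% (9 to 15 patients), with 1% to 10% (3 to 30 patients) as a wider range. It should be low, because Protocol 4.5.6.1 plans baseline imaging for every patient within 28 days before randomization.
- Proportion dead, planned: SAP Table 3 projects 60 deaths at the primary PFS analysis, and 60/300 = 20%.
- Proportion dead, reported: Protocol 1.2.2.2 describes OS at the primary cutoff as immature, with events below 10%. I read this as under 10% of patients having died, and use 10% as an upper value.

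| Without central baseline | Deaths lost at 10% | Deaths lost at 20% |
|---|---|---|
| 1% (3 patients) | 0.3 | 0.6 |
| 3% (9 patients) | 0.9 | 1.8 |
| 5% (15 patients) | 1.5 | 3.0 |
| 10% (30 patients) | 3.0 | 6.0 |

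**Effect on information.** The documents do not plan an IRC event count, so 166 serves only as a yardstick. Losing 0.6 to 6 events from 166 changes nominal power from 80.1% to between 80.0% and 78.6%.

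**The case against.** The strongest reply is that the sentence is ambiguous, not contradictory. Part (ii) says it repeats 5.3.2, and 5.3.2 censors only patients without an event. On that reading the added sentence supplies only a censoring date for patients the IRC cannot assess, and deaths stay governed by 5.3.2. This may be what the authors meant. A reader might infer that the SAP deliberately censors deaths; it does not say so, and never mentions death in that sentence. But the condition that triggers the rule is missing scans, with no restriction to event-free patients, so the text does not deliver the benign reading either. IRC procedures are in a separate charter that is not available here. It might clarify the point, but the SAP does not refer to it for this rule.

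A second reply is that the alternative has a cost. If deaths count and survivors are censored at day 1, whether a patient without a baseline stays in the risk set depends on the outcome, and that patient is treated as progression-free until death. Censoring all such patients at day 1 treats them alike. This is a real drawback, but 5.3.2 already accepts the same asymmetry for patients with no post-baseline assessment, so it does not explain why the IRC analysis should differ.

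A third reply is that restoring deaths will not make the two analyses fully comparable, because investigator-assessed progressions in these patients will still be absent from the IRC analysis. That is correct. It is also why a reader should not conclude that all observed PFS events are wrongly discarded: without a baseline the IRC cannot determine progression, and that loss comes with the endpoint.

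**Conclusion.** The point stands in a narrow form. As worded, SAP 5.3.4(ii) is inconsistent with the PFS definition and with 5.3.2 and 5.3.3, because it makes no exception for death in patients without baseline scans.

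The size is small. With 3% to 5% of 300 patients lacking a central baseline and at most 10% dead at the cutoff, about one death is lost (0.9 to 1.5). The planned 20% death rate would give two to three (1.8 to 3.0), but the maturity reported in Protocol 1.2.2.2 makes the lower figure more likely. Both rest on the assumed 3% to 5%, for which the documents give no source.

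A reader might also infer that the trial's conclusion is at risk. The documents do not support that: the rule touches a sub-case of one sensitivity analysis, and neither the primary test nor the PFS-then-OS hierarchy in SAP 2.1 uses it.

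**What to change.** Replace the sentence in 5.3.4(ii) with a rule along these lines: patients without baseline scans at the IRC who die by the CCOD are IRC-PFS events at the date of death; all other patients without baseline scans are censored one day after randomization. Report the number of patients and deaths affected, by arm. If the count is not trivial, show the IRC result under both rules, because survivors without a baseline leave the risk set at day 1 while deaths stay in.

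The cost is one sentence and a short table. Death dates are already collected for OS, so no new data are needed. Since Protocol 1.2.2.2 shows that the primary analysis has been done, the sponsor should also confirm how deaths in these patients were handled in any IRC analysis already run.

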5.3.5 Supplementary Analyses for Primary Endpoint

Two supplementary analysis as outlined below based on different strategy of handling ICE are planned for PFS. Note that the attributes of population, variables and population level summary will remain the same as the primary estimand. The analysis for the supplementary estimands will be conducted only on the primary endpoint investigator assessed PFS.

1. **PFS assessed by investigator based on hypothetical strategy for use of any NPT prior to disease progression:** → To assess the impact of use of any NPT prior to disease progression, the primary analysis of investigator assessed PFS will be repeated with the ICE of use of any NPT handled using a hypothetical strategy. According to this strategy, patients who start NPT prior to disease progression will be censored at the time of the last disease status assessment before the initiation of NPT. If patients start any NPT before starting study treatment then the data of those patients will be censored at the time of randomization plus day 1. Approaches to handle other ICE (Discontinuation of study treatment prior to disease progression) and analysis method will be the same as mentioned in section [5.3.2](#).
2. **PFS assessed by investigator based on composite strategy for use of any NPT prior to disease progression:** → In addition to above estimand, here supplementary estimand for PFS will be estimate by following composite strategy. According to composite strategy, use of any NPT prior to disease progression will be considered as PFS event (progressed) at the time of initiation of NPT. If patients start any NPT before starting study treatment then the data of those patients will be censored at the time of randomization plus day 1. Approaches to handle other ICE (Discontinuation of study treatment prior to disease progression) and analysis method will be the same as mentioned in section [5.3.2](#).

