4.3.2 Study Treatment Dosage, Administration, and Compliance

The treatment regimens are summarized in Section 3.1.1. Patients should receive the first dose of study drug on the day of randomization, if possible. If this is not possible, the first dose should occur no later than 3 days after randomization.

Refer to the pharmacy manual for detailed instructions on drug preparation, storage, and administration.

Details on treatment administration (e.g., dose and timing) should be noted on the Study Drug Administration electronic Case Report Form (eCRF). Cases of overdose, medication error, drug abuse, or drug misuse, along with any associated adverse events, should be reported as described in Section 5.3.5.12.

At the beginning of each patient's study participation, site study staff will provide the patient with detailed instructions and training for the handling and administration of study drugs. Patients will receive and should be instructed to complete a medication diary. For GDC-9545 and any other study drug administered at home, the medication diary, unused study drug, and study drug containers (used or unused) should be collected and reviewed for drug accountability at the beginning of each cycle.

Capsules (or tablets, as applicable) that are not returned will be considered to have been taken, unless otherwise specified in the patient's diary/eCRF. Note that dosing eCRFs should be completed using the following prioritization (in the event of discrepancies): 1) site pharmacy drug accountability logs (IMP dispensed minus IMP returned); 2) patient daily dosing diary; and 3) clinic visit patient interview notes.

Guidelines for treatment interruption or discontinuation for patients who experience adverse events are provided in Section 5.1.3.

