4. ANALYSIS SETS

The following analysis sets are defined:

Population	Definition
Full Analysis Set	All participants assigned to treatment groups as randomized by the IxRS.
Safety-evaluable	All participants randomly assigned to study treatment and who received at least one dose of study treatment.
ctDNA-evaluable	All participants assigned to treatment groups as randomized by the IxRS with evaluable plasma ctDNA at baseline.
PRO-evaluable	All randomized participants who have a baseline and at least one post-baseline PRO assessment.
PK-evaluable	All randomized participants in the GDC-9545 arm who have at least one evaluable GDC-9545 plasma concentration.

ctDNA = circulating tumor DNA, PRO = patient reported outcome, PK = pharmacokinetic.

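### The composite-strategy PFS analysis censors non-protocol therapy started before study drug, although its own rule makes that therapy an event

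*SAP*

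**What the plan says.** SAP Section 5.3.5 plans two supplementary PFS analyses that differ from the primary one in how they handle NPT.

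- **Item 1, hypothetical strategy.** Patients who start NPT before progression "will be censored at the time of the last disease status assessment before the initiation of NPT".
- **Item 2, composite strategy.** Here "use of any NPT prior to disease progression will be considered as PFS event (progressed) at the time of initiation of NPT".

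Both items then carry the same sentence, about those who "start any NPT before starting study treatment then the data of those patients will be censored at the time of randomization plus day 1". The point concerns its second occurrence, in item 2. No reason for the exception is given.

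The introduction to Section 5.3.5 adds that the "attributes of population, variables and population level summary will remain the same as the primary estimand".

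The surrounding definitions are:
- The intercurrent event is "Use of any non-protocol anti-cancer treatment (NPT) prior to disease progression as detailed in Protocol section 4.4.3" (SAP 5.3.1), with no condition that study drug has been started.
- PFS is "defined as time after randomization to the first occurrence of disease progression or death from any cause" (SAP 5.3.1).
- The Full Analysis Set is "All participants assigned to treatment groups as randomized by the IxRS" (SAP 4).
- If dosing on the day of randomization is not possible, "the first dose should occur no later than 3 days after randomization" (Protocol 4.3.2). Appendix 1, footnote c, gives this limit as 3 business days.

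**The concern.** Under a composite strategy the intercurrent event becomes part of the endpoint. A patient randomized to one arm who takes other anti-cancer therapy without starting the assigned drug is a plain case of what item 2 sets out to count. The exception makes that patient a censored observation at day 1 with no information.

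Two things follow. The analysis labelled composite does not estimate its own estimand for these patients. And because items 1 and 2 then handle them identically, comparing the two analyses says nothing about how sensitive PFS is to this kind of NPT.

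There is also a wording problem. The variable cannot stay the same as in the primary estimand once NPT start counts as an event.

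**Working it through.** **1. Are these patients inside the composite definition?** Yes. The intercurrent event is any NPT before progression, the clock starts at randomization, and everyone randomized is analysed. NPT begun after randomization and before first dose meets all three conditions.

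**2. Why the sentence fits item 1 but not item 2.** Item 1 censors at the last assessment before NPT. The first scheduled post-baseline scan is at 8 weeks (Protocol 4.5.6.2), so a patient who takes NPT before first dose would normally have none by then. SAP 5.3.2 censors patients with no post-baseline assessment at randomization plus 1 day. In item 1 the sentence therefore agrees with the general rule. In item 2 the general rule gives an event and the sentence gives a censoring.

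**3. A logical check.** The composite time is min(time to progression or death, time to NPT). Such an analysis can add events to the primary analysis or bring them forward, but it cannot remove any. Take a patient who starts NPT on day 2, is never dosed, and progresses at month 4:

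| Analysis | Status | Time |
|---|---|---|
| Primary (treatment policy, SAP 5.3.1) | event | month 4 |
| Item 1, hypothetical | censored | day 1 |
| Item 2, as written | censored | day 1 |
| Item 2, by its own general rule | event | day 2 |

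The progression would be observed, because Protocol 4.5.6.2 continues tumor assessments after new anti-cancer therapy. Item 2 as written loses it.

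**4. The plan's own figures.** The SAP gives none for the composite analysis. The primary design reproduces:
- Hazard ratio: 5.5/8.5 = 0.647.
- Events: 4(1.960 + 0.842)²/(ln 0.647)² = 165.6, so 166, with power 80.1%.
- Largest significant hazard ratio: exp(−1.960 × 2/√166) = 0.738.

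**5. Size.** Trials of 300 patients were simulated with exponential PFS, SAP Table 2 accrual, 10% annual loss to follow-up, cutoff at the 166th event and an unstratified Cox model. Chosen patients were either censored at day 1 (as written) or counted as events at day 1 (general rule). The number affected is an assumption. There were 600 trials per row, or 200 for rows marked *.

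| True HR | Affected patients | As written | As event |
|---|---|---|---|
| 0.647 | 1 control | 0.649 | 0.643 |
| 0.647 | 3 control | 0.645 | 0.626 |
| 0.647 | 5 control | 0.645 | 0.614 |
| 0.647 | 10 control | 0.648 | 0.589 |
| 0.647 | 1 GDC-9545* | 0.647 | 0.657 |
| 0.647 | 4 GDC-9545* | 0.643 | 0.682 |
| 0.647 | 4 per arm* | 0.643 | 0.656 |
| 0.647 | 5 per arm | 0.641 | 0.658 |
| 1 | 5 control | 1.000 | 0.942 |
| 1 | 10 control | 1.000 | 0.888 |
| 1 | 5 per arm | 1.001 | 1.001 |

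Each affected patient adds exactly one event. The sign of the shift depends on the arm.

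**6. How many in the reported data?** Protocol 1.2.2.2 gives percentages but no denominators. Among denominators from 140 to 163:
- The adverse-event percentages (84.7, 13.3, 1.3 and 71.1, 8.6, 2.0) fit only 150 GDC-9545 and 152 control patients, for example 127/150 and 108/152.
- The clinical benefit and response rates fit only 151 and 152 (48/151 and 19/151; 32/152 and 11/152), and 151 + 152 = 303, the number enrolled.

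That implies one untreated patient, in the GDC-9545 arm. It assumes that treatment received equals treatment assigned. The documents do not say whether this patient took NPT.

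**The case against.** The case for leaving the text alone is mainly that little hangs on it. The analysis is supplementary, carries no alpha and has no place in the PFS-then-OS hierarchy. The window from randomization to first dose is a few days. The primary analysis ignores NPT and keeps these patients' later data. All of that stands, and it limits this to a minor correction.

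The objection on the remedy also stands. Dating the event at NPT start is not enough alone. NPT begun on the day of randomization would have time zero, and NPT begun earlier would have negative time. The SAP phrase sets no lower limit, and Protocol 4.4.3 also covers therapy taken before study treatment.

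It can be said too that the remark about unchanged variables is loose drafting, since item 2 tells a programmer what to count. That is fair, but the estimand should still be stated correctly.

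A reader might infer that, because the trial is open-label, refusals cluster in the control arm, so the rule hides control events and the composite hazard ratio is biased in a known direction. The documents do not support this. No section reports or predicts control-arm refusal, the control drug is chosen by the physician, and the reported percentages place the one apparently untreated patient in the GDC-9545 arm.

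**Conclusion.** The two sentences in item 2 conflict, and the censoring sentence is wrong for the composite estimand. That rests on the text alone and is firm.

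The numerical effect is small and of no fixed sign: about 0.01 on the hazard ratio for one patient, about 0.02 to 0.06 for 3 to 10 patients all in control, and toward 1 if they are in the GDC-9545 arm or equally split (with a true hazard ratio below 1). These sizes rest on assumed counts and on exponential PFS without stratification. For the reported data, at most about one patient seems to be concerned, and perhaps none.

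A reader might also infer that the primary PFS result is in doubt. It is not: the treatment-policy analysis, the 166 events and the significance level are untouched. The rule remains in force for the China subpopulation, because SAP 5.7.6 applies the methods of Sections 5.1 to 5.7 there when data allow, though without formal testing.

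**What to change.** In SAP 5.3.5, item 2:

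1. Replace the censoring sentence with: NPT started after randomization and before study treatment, including in never-dosed patients, is a PFS event at the NPT start date, or at randomization plus 1 day if NPT started on the day of randomization.
2. State separately that NPT begun before randomization is not a post-randomization intercurrent event and is handled as a protocol deviation.
3. State that the composite variable is the first of progression, death or NPT start, and limit the remark about an unchanged variable to item 1.

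Keep day-1 censoring in item 1 only. The cost is a few sentences, a short change to the event and date derivation, and a rerun of one supplementary analysis if any patient qualifies. No new data are needed beyond the NPT start date, which the analysis already uses.
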